7.4.3 Clinical Laboratory Assessments

Blood and urine samples will be collected for the following clinical laboratory tests, following the timing noted in the Schedule of Assessments (Table 1, Table 2, and Table 3). All samples should be clearly identified. Sample collection, preparation, and handling/shipment procedures are described in the Laboratory Manual.

Table 8 Clinical Safety Laboratory Evaluations

Type of Evaluation	Tests			
Biochemistry	 Albumin Aspartate aminotransferase Alanine aminotransferase Alkaline phosphatase γ-Glutamyl-transferase Lactate dehydrogenase 	 Bilirubin (total) Protein (total) Creatinine and eGFR calculation Amylase Lipase Total carbon dioxide Blood urea nitrogen Glucose 	 Sodium Potassium Chloride Calcium Magnesium Phosphate 	
LFT visits	 Aspartate aminotransferase Alanine aminotransferase Alkaline phosphatase γ-Glutamyl-transferase 	Bilirubin (total)		
CCI				
Hematology	Hematocrit Hemoglobin Red blood cell count ESR Mean corpuscular volume Mean corpuscular hemoglobin Mean corpuscular hemoglobin concentration Reticulocyte count	Platelet count White blood cell count cell counta Immunoglobulin and subclass concentrationsa,b	White blood cell differentials and absolute counts:	
Coagulationa	International normalized ratPartial thromboplastin time	tio		
Urinalysis/ microscopy ^c and urine chemistry	pHNitriteUrobilinogenBilirubin	GlucoseKetone bodiesProtein	 βhCG (women only)^a Microscopy^c (white blood cells, red blood cells, casts) Protein/creatinine ratio^d 	

Evobrutinib (M2951) A Study of Efficacy and Safety of M2951 in Relapsing Multiple Sclerosis MS200527_0086

Additional urine testing	βhCG (women only) ^a		
Other Screening tests ^e	HCV antibodies Serum βhCG (women only)	 HBV IgM antibodies HIV^f FSH 	HBsAgQuantiferon tuberculosis test

ALT=Alanine aminotransferase, AST=Aspartate aminotransferase, $\beta hCG=\beta$ -human chorionic gonadotropin, CMV=cytomegalovirus, EA=early antigen, EBNA=Epstein-Barr nuclear antigen, EBV= Epstein-Barr virus, eGFR=estimated glomerular filtration rate, ESR=erythrocyte sedimentation rate, FSH=follicle-stimulating hormone, GGT= γ -glutamyl-transferase, HAV=hepatitis A virus, HBc=hepatitis B core antigen, HBsAg=hepatitis B surface antigen, HBV=hepatitis B virus, HCV=hepatitis C virus, HEV=hepatitis E virus, HIV=human immunodeficiency virus, hsCRP=high sensitivity C-reactive protein, IDMC=independent data monitoring committee, Ig=immunoglobulin, LFT=liver function test, CCl PCR=polymerase chain reaction, ViRNA=virus RNA, VCA=viral capsid antigen.

- a. To be done only when specified in Table 1, Table 2, and Table 3, and not as a standard laboratory evaluation.
- b. Results will not be disclosed to the sites, Sponsor, or representative, to avoid unblinding. However, the IDMC will have access to these data as applicable.
- c. Microscopy will be performed only if urine dipstick is abnormal.
- d. Protein/creatinine ratio will only be determined at the central laboratory if urine dipstick is abnormal
- e. Performed only at Screening.
- f. HIV testing will be done at Screening only where required as per local regulation.

7.4.4 Vital Signs, Physical Examinations, and Other Assessments

7.4.4.1 Vital Signs

Vital signs, including semisupine blood pressure, pulse rate, respiratory rate, weight, and oral temperature will be assessed predose at all specified trial visits (Table 1, Table 2, and Table 3). Height will be measured at Screening only.

A semiautomated pulse rate and blood pressure recording device with an appropriate cuff size will be utilized. Pulse rate and blood pressure will be measured after 10 minutes rest in the semisupine position with the participant's arm unconstrained by clothing or other material. The blood pressure should be assessed on the same arm for each participant throughout the trial.

7.4.4.2 Physical Examinations

Physical examinations will be assessed at each site as indicated in Table 1, Table 2, and Table 3. Physical examination includes assessment of the following: general appearance, skin, head and neck, mouth, lymph nodes, thyroid, abdomen, and musculoskeletal, cardiovascular, and respiratory systems. Physical examination findings during Screening before obtaining informed consent will be recorded as medical history events and new findings or worsening during the trial as AEs. Records from physical examinations will be retained at each site and will not be captured in the eCRF.

7.4.4.3 12-Lead ECG and Chest X-ray

A 12-lead ECG will be performed during Screening. For participants in the OLE Period, a 12-lead ECG will also be conducted at OLE Day 1, unscheduled visits, Week 48, and then every 48 weeks

up to and including the OLE End of Treatment Visit. The 12-lead ECG recordings will be obtained after 10 minutes of rest in a semisupine position.

The following ECG parameters will be obtained directly from the computerized 12-lead ECG recordings: rhythm, ventricular rate, PR interval, QRS duration, and QT interval. The corrected QT interval will be calculated using Fridericia's formula. The overall evaluation (normal/abnormal) will be recorded on the eCRF, and if abnormal, the specific abnormality will be recorded. Abnormal evaluations will be judged as clinically significant or not clinically significant by the Investigator.

The printout of the ECG is to be signed, dated, and filed in the Investigator's Site File along with a signed and dated copy (if the printouts are not on archive-quality paper).

Posteroanterior CXRs will be performed during Screening according to local standard practice. For participants in the OLE Period, a CXR will be performed at OLE Day 1. Participants who had a CXR performed for clinical reasons within 3 months prior to Day 1 do not need to have the CXR repeated. The CXR should show no evidence of active infective process, or any other clinically significant abnormalities. The overall evaluation (normal/abnormal) will be recorded on the eCRF, and if abnormal, the specific abnormality will be recorded. Abnormal evaluations will be judged as clinically significant or not clinically significant by the Investigator.

[figure not shown]
The 12-lead ECG and CXR will be performed and read locally.

[figure not shown]
7.4.5 Total Immunoglobulin Assessments

Blood samples for Ig levels (IgM, IgA, and IgG) will be collected as noted in Table 1, Table 2, and Table 3.

[figure not shown]
Samples will be analyzed by the central laboratory selected by the Sponsor. Samples will be collected, labeled, processed, stored, and shipped according to the instructions in the Laboratory Manual.

[figure not shown]
Results will not be disclosed to the sites, Sponsor, or representative, to avoid unblinding. However, the IDMC will have access to these data as applicable.

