Study Day ± Visit Window	756, 840, 924 ±7	1008 ±7	1092, 1176, 1260 ±7	1344 ±7	1512 ±14	1680 ±14	1848 ±14	2016 ±14	2184 ±14	2352 ±14	2520 ±14		2688 ±14	2716 ±7
C-SSRS (Since Last Visit Scale)		Х		Х		Х		Х		Х			Х	

AE=adverse event, C-SSRS=Columbia-Suicide Severity Rating Scale, ECG=electrocardiogram, eCRF=electronic Case Report Form; EDSS=expanded disability status scale CCI , CCI , Ig=immunoglobulin, IMP=investigational medicinal product, LFT=liver function test, MRI=magnetic resonance imaging, CCI , OLE=Open-label Extension, CCI ; CCI ;

- Physical exams will be performed every 24 weeks (Weeks 120, 144, 168, 192, 216, 240, 264, 288, 312, 336, and 360) and at unscheduled visits.
- b. The following will be obtained predose: vital signs (Section 7.4.4.1), hematology and chemistry (Table 8), and total Ig levels (IgM, IgA, IgG) (see Section 7.4.5).

CC

- d. Blood samples for Ig levels will be obtained predose every 24 weeks (Weeks 120, 144, 168, 192, 216, 240, 264, 288, 312, 336, 360, and OLE End of Treatment).
- e. Urine samples for urinalysis will be obtained predose every 24 weeks (Weeks 120, 144, 168, 192, 216, 240, 264, 288, 312, 336, 360 and OLE End of Treatment), at the 4-week Safety Follow-up/End of Trial Visit, and at unscheduled visits. If local urinalysis by dipstick is abnormal, urine microscopy should be performed by a central laboratory. If at least 1+ protein is detected, urine protein/creatinine ratio should be determined.
- The participant will have Telephone Visits at regular intervals between on-site visits. For details of Telephone Visits, please see Section 7.1.6.1. The phone calls have a window of ± 1 week, and will occur at Week 102, Week 114, Week 126, Week 138, Week 150, Week 162, Week 174, Week 186, Week 200, Week 208, Week 224, Week 232, Week 248, Week 256, Week 272, Week 280, Week 296, Week 304, Week 320, Week 328, Week 344, Week 352, Week 368, Week 376. Confirmation of completion of monthly home pregnancy testing and discussion of results can be included in these calls if they are scheduled to occur during the same week.

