2 Sponsor, Investigators and Trial Administrative Structure

This clinical trial will be sponsored by:

- EMD Serono Research & Development Institute, Inc., Billerica, Massachusetts, USA.
- Merck KGaA, Darmstadt, Germany in countries outside the USA.

The trial will be conducted at approximately 64 sites in Western and Eastern Europe, in USA, and RoW. For the OLE Period, enrollment will continue at the sites used during the Screening and Treatment periods.

The Coordinating Investigator, PPD, represents all Investigators for decisions and discussions regarding this trial, consistent with the International Council for Harmonisation (ICH) Topic E6 Good Clinical Practice (GCP; hereafter referred to as ICH GCP). The Coordinating Investigator will provide expert medical input and advice relating to trial design and execution and is responsible for the review and signoff of the clinical trial report.

Signature pages for the Protocol Lead and the Coordinating Investigator as well as a list of Sponsor responsible persons are in Appendix I.

The trial will appear in the following clinical trial registries: ClinicalTrials.Gov and EUDRACT.

The Sponsor will enlist the support of a CRO, to conduct the clinical part of the trial including trial set-up, operation of an IWRS for randomization, coordination, monitoring, medical oversight, data capture, data management, statistical analysis, and clinical trial reporting. The Sponsor will also make use of the CRO's central laboratory for sample analyses, storage, and shipment to specialized bioanalytical laboratories. The Sponsor will supervise all outsourced activities.

An IDMC will be responsible for safety monitoring until the last randomized participant completes the blinded phase. The IDMC will consist of at least the following core members: 2 clinicians and 1 biostatistician. The full list of IDMC members and responsibilities will be included in the IDMC charter. After the blinded phase, a switch to an internally convened SMC will be considered. The SMC will consist of at least the following members: Sponsor and CRO medical advisor, Sponsor biostatistician, Sponsor Drug Safety Physician, Sponsor Clinical Pharmacology representative and Coordinating Investigator. An SMC charter will be provided once the transition from the IDMC has been completed.

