Only when the last participant reaches 24 weeks of treatment or discontinues from treatment prematurely, the protocol violations are determined, and the database is partially locked for the primary analysis will the drug codes be broken and made available for the primary data analysis. At that point, the CRO and Sponsor study teams will be unblinded to treatment. Dissemination of results from the primary analysis will be limited to senior management. There will be no communication of primary analysis results to the sites.

After the primary analysis, the study will continue as a blinded extension until the Week 52 Analysis occurs, with participants, site staff, and the Investigator blinded to M2951 dose group, and with the Assessing Neurologist and central MRI reader blinded to all treatments. For participants entering the OLE Period at the End of Treatment Visit (Week 48), the data will no longer be blinded.

All breaks of the trial blind must be adequately documented.

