17.7 Pregnancy Test

Results of pregnancy test (urine or serum) will be listed for OLE period based on SAF-OLE.

Analyses will be performed for the DBP+OLE period based on the SAF analysis set and for OLE period based on the SAF-OLE.

Data on immunoglobulin (Ig) levels, and CCl (see list of parameters in Appendix 19.2) will be summarized for the OLE period for observed values, change from OLE baseline values, and percent change from OLE baseline by treatment group and overall using descriptive statistics.

In addition, number and percent of subjects falling above, below, and within normal range will be summarized where applicable. Assessments made at the End of Treatment visit for treatment discontinuers will be windowed appropriately. Assessments made at the End of Trial visit for study discontinuers will be summarized separately from assessments made at Safety follow-up visit at OLE Week 388 End of Trial visit for study completers.

Additionally, descriptive statistics of absolute values of CCI will be provided for subjects falling above, below, and within normal range of the specific laboratory parameter. Summaries will be provided on OLE period for observed values, change from OLE baseline values, and percent change from OLE baseline by treatment group and overall.

Shift tables from OLE baseline value (low, normal, high) to end of OLE Period will be presented by treatment group and overall, for each Ig class and subclass, and parameters where applicable (see list of parameters in Appendix 19.2), using SAF-OLE analysis set.

[figure not shown]
Boxplots for each Ig class and subclass, (g/L), and CC (see list of parameters in Appendix 19.2) by treatment group and time point will be provided, for OLE period.

Line plots of median percent change from baseline will be provided by time point and treatment group on DBP and OLE combined periods for each Ig class and subclass, and (see list of parameters in Appendix 19.2).

(see list of parameters in Appendix 19.2) and Ig class and subclass levels will be listed by treatment group, participant and time point (where applicable). IgG values < 3 g/L (severe hypogammaglobulinemia) and IgG values < 6 g/L (hypogammaglobulinemia) will be flagged in the listing.

EAIR of infections

For definition of severe infections AESI, see Section 17.2.3 and Appendix 19.5.

Confidence interval of incidence rate will be calculated using the Garwood method for Poisson mean.

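### The protocol's immunoglobulin non-disclosure rule has no end date: in the open-label extension it outlasts the blind and leaves no stated route to the treating investigator

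*Protocol*

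**What the plan says.** Protocol Section 7.4.5 sets the scope: "Blood samples for Ig levels (IgM, IgA, and IgG) will be collected as noted in Table 1, Table 2, and Table 3". Table 1 is the main study; Tables 2 and 3 are the OLE. The same section continues: "Results will not be disclosed to the sites, Sponsor, or representative, to avoid unblinding". It names one exception: "However, the IDMC will have access to these data as applicable". Table 8 footnote b (Section 7.4.3) repeats both sentences.

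On who oversees safety, Protocol Section 2 says: "An IDMC will be responsible for safety monitoring until the last randomized participant completes the blinded phase". After that, a move to an internal Safety Monitoring Committee (SMC) is only to be considered. Its minimum membership is Sponsor and CRO staff plus the Coordinating Investigator.

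On blinding, Protocol Section 6.9 unblinds the CRO and Sponsor study teams at the primary analysis and adds: "For participants entering the OLE Period at the End of Treatment Visit (Week 48), the data will no longer be blinded".

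Sampling goes on late into the OLE. Table 3 footnote d says: "Blood samples for Ig levels will be obtained predose every 24 weeks", with the last sample at the OLE End of Treatment Visit. Section 8.3.4 makes Ig level an OLE safety endpoint. The SAP's section on immunoglobulin levels (17.8 in its table of contents) provides a listing in which "IgG values < 3 g/L (severe hypogammaglobulinemia) and IgG values < 6 g/L (hypogammaglobulinemia) will be flagged in the listing".

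**The concern.** The rule is justified by the blind but not limited to it. Once a participant is on open-label M2951 and the blinded phase is over, withholding the result protects nothing. Read literally, it still keeps a safety laboratory value from the physician responsible for that participant, and the one body allowed to see it has finished its stated task.

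Protocol Section 3.2 lists serious and opportunistic infections among the potential risks under close Sponsor monitoring, and SAP Section 17.2.3 makes serious or Grade 3 and higher infections, and opportunistic infections, events of special interest. Ig level is a natural aid to interpreting such events. The OLE is also the longest exposure period in the trial.

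Data quality is at stake too. Under Section 7.4.1.1 a laboratory abnormality can become an adverse event when the investigator judges it medically important. That route cannot work for a value the investigator does not receive.

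**Working it through.** **1. Number of results covered, starting from the plan's own figure.**
- Protocol Appendix II gives 17 Ig samples of 5 mL in the OLE, 85 mL in total.
- Table 2 has Ig at OLE Weeks 0, 24, 48, 72 and 96: 5 samples.
- Table 3 footnote d has Ig every 24 weeks from Week 120 to Week 360: (360 − 120)/24 + 1 = 11. The OLE End of Treatment Visit (Week 384) makes 12.
- 5 + 12 = 17, and 17 × 5 mL = 85 mL. The Appendix II figure is reproduced.
- 17 − 1 = 16 of these fall after OLE Day 1. For participants coming from M2951, OLE Day 1 is also the main-study Week 48 visit (note to Figure 2).
- The SAP's Ig analysis windows stop at OLE Week 336, so Weeks 360 and 384 have none: 17 − 2 = 15.

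**2. Does the rule reach the OLE?** Yes. Section 7.4.5 cites all three schedules and sets no time limit. Table 8 footnote b sets none either.

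**3. Does the reason reach the OLE?** Not for the participant concerned. All OLE participants receive M2951 (Section 7.1.6), and Section 6.9 says their data are no longer blinded. While other participants remain in the blinded extension, a case for withholding can still be made. It ends when the last of them finishes.

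**4. Does the named reader reach the OLE?** Only in part. The IDMC stays until every randomized participant has left the blinded phase, so it overlaps with the OLE time of early entrants. After that, Section 2 offers a possible SMC made up largely of Sponsor and CRO members, and the rule excludes the Sponsor and its representative. The hepatology committee reviews suspected liver injury and does not fill an Ig gap.

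**5. Does other text open a route?** None names Ig access in the OLE, and three places pull against the rule:

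| Place | What it provides | Against 7.4.5 read literally |
|---|---|---|
| Protocol Section 7, introduction | The Treating Investigator sees safety data and decides treatment partly on laboratory findings | Ig is a safety laboratory test in Table 8, yet it is withheld |
| Protocol 8.5.4.1, applied to the OLE by 8.5.4.3 | All safety variables are listed by participant and time point | The Sponsor must eventually hold values the rule denies it |
| Protocol 3.2 | IDMC, SMC and hepatology committee keep reviewing the safety data available to them | Does not say that withheld Ig data become available |

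The second row matters most. The non-disclosure sentence cannot be meant to last indefinitely, but nothing says when it stops.

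**The case against.** The strongest reply is that the sentence carries its own limit. It exists to protect the blind; Section 6.9 lifts the blind on OLE entry; and Section 8.5.4.1 requires participant-level listings that the Sponsor will hold. On that reading this is leftover wording, and in practice the restriction ended with the blind. That is plausible, but no passage says so. A central laboratory or site following 7.4.5 and Table 8 to the letter would keep withholding.

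A reader might also infer something stronger: that nobody could act on a falling IgG for 384 weeks, and that a value under the SAP's 3 g/L flag would come to light only in an end-of-study listing. The documents do not support this:
- The IDMC overlaps with early OLE time, and an SMC is foreseen.
- SAP Section 8 reports that OLE interim analyses at Week 60 and Week 240 were already conducted. Protocol Section 8.6 plans selected safety endpoints for both OLE interim analyses. Whether Ig was included can be neither shown nor excluded from these documents.
- The committee charters and the Laboratory Manual are not available here and could set Ig access.
- Nothing bars an investigator from ordering a local IgG test.

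Two limits on size also stand. Multiplying 17 samples by the roughly 200 expected OLE participants gives 3,400 results, but that assumes nobody leaves before Week 384. Participants may transfer to the long-term follow-up study, and SAP Section 5 reports early termination. Further, no passage reports an Ig decline under M2951, and Section 3.2 says no causal link to infections has been established.

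**Conclusion.** The point holds as a defect in the written rule. Non-disclosure has no end date, reaches the OLE schedules, outlives its stated reason, and has one named reader whose role ends with the blinded phase. Up to 17 scheduled OLE Ig results per participant therefore have no stated route to the treating investigator. That count is a planned maximum for someone who stays to Week 384; it is lower for anyone who leaves earlier.

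The conclusion rests on the protocol and SAP alone. It does not claim that results were in fact unseen, that any participant was harmed, or that Ig decline is an established risk. If a charter or the Laboratory Manual already releases OLE Ig results, the protocol text contradicts practice and still needs correcting. Because the SAP describes a study closing early, the benefit is confined to participants still being followed under this protocol.

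**What to change.** Reconcile Section 7.4.5 and Table 8 footnote b with Sections 2 and 6.9:

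- Limit non-disclosure to the period before the last randomized participant has finished the blinded phase. This keeps whatever blind remains for those still in it.
- State that OLE Ig results are then released to the investigator and to the body overseeing OLE safety, and name that body.
- Align the SMC charter and the Laboratory Manual with the new wording.

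No IgG threshold, alert limit or clinical action is proposed. The SAP's 6 and 3 g/L flags annotate a listing, and nothing in the documents gives them another use.

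The cost is small: two sentences in an amendment, a change to central-laboratory reporting, and some added queries from sites. No new samples or visits are needed.

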7.8 Columbia-Suicide Severity Rating Scale

The C-SSRS will be used for prospective suicidality assessment. The C-SSRS will be a tool used at Screening to identify eligible participants. The C-SSRS will be measured in all participants as indicated in Table 1, Table 2, and Table 3. The C-SSRS Screening Scale will be used in the main study and C-SSRS Since Last Visit Scale will be used in the OLE. The structured interview prompts recollection of suicidal ideation, including the intensity of the ideation, behavior and attempts with actual/potential lethality.

The scale will be administered by the Treating Investigator or a qualified designee. Please note that assessing the risk of suicide is a difficult and complex task when applied to the individual patient. No single clinical scale can replace a thorough medical examination and suicide risk assessment. Ultimately, the determination of the presence of suicidality depends on clinical judgment.

8 Statistics

